## 9.4 Interim Analyses and Stopping Rules

We acknowledge that of the rationale for superiority of IVR CBT has diminished because instead of in-person treatment, control participants can now obtain videoconference or telephone CBT-CP from their homes. However, we still expect IVR CBT will be superior. We assume that dose will be greater in the IVR condition because patients can access treatment at any time, not just during business hours and session time is shorter reducing therapist and participant burden relative to the control condition. Time to treatment will be shorter in IVR because the centralized delivery of IVR CBT allows more efficient use of therapist resources. There is relatively little information reported in the literature about dose in videoconference treatment and none about time to treatment relative to in-person treatment so there is little information to guide these estimates more precisely. We have proposed to monitor these and other factors that we believe will continue to be different, and show an advantage for the IVR condition, as part of the trial (see below).

**Monitoring Separation Between Arms:** We will monitor indicator variables (below) on treatment delivery, uptake and quality to determine whether the treatment arms are diverging in ways expected to drive differences in clinical outcomes. We will continuously monitor the indicators and calculate the means and confidence intervals of each indicator for both groups and for the difference between groups. These data will be shared with the DSMB at the regularly scheduled DSMB meetings occurring every 4 months and at 50% of participant treatment completion and used to assess whether there is divergence between the treatment conditions. These data may be used to inform a future futility analyses if needed once adequate data is collected [50% participants (n=382) completed treatment].

Indicator	Description
Dose	# of sessions/weeks attended including only those with $\geq 1$ session
Engagement	% who initiate treatment (attend first treatment session)
Minimal dose	% who achieve minimal dose (minimal dose=3 sessions/weeks)
Time to treatment initiation	Time from randomization to first treatment session or IVR call among those with $\geq 1$ session
Quality assurance	Ratio of #skills taught/#sessions among those with $\geq 1$ session

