## **9.6 Data Analyses**

Quantitative Analysis. As an estimate of uptake, we will present the proportion of patients who agree to be randomized out of all who are offered referral to treatment in our study. Randomization success will be assessed by side-by-side summaries of

baseline demographic and clinical characteristics of subjects by treatment group. Analyses of all outcomes will be done according to the intent-to-treat principle.

Primary Analysis. We will test and estimate the difference between COPES and CBT-CP in terms of BPI interference by using a linear mixed-effects model which simultaneously models all available BPI interference measurements including baseline. The model will contain fixed effects for treatment (categorical: COPES vs. CBT-CP), site (categorical), gender (categorical), time (categorical: baseline, 1, 4, 6, 12 months), and the treatment-by-time interaction. The only covariates that will be included in the primary and secondary analysis (including subgroup analyses) are site and gender. We are adjusting for these 2 variables because they are used for stratification in randomization. An unstructured variance-covariance matrix will be used to model correlations among repeated measures within a subject, and a therapist random effect will be used to model the correlation of outcomes in subjects who share the same therapist. Because this is a randomized trial, in the model above we will impose the constraint that the means for the two groups are equal at baseline (that is, we will perform a constrained longitudinal data analysis). Following the CONSORT recommendations, we will not perform any test for baseline differences as these tests are not needed in a randomized clinical trial “Such significance tests assess the probability that observed baseline differences could have occurred by chance; however, we know that any differences are caused by chance” This model will allow us not only to assess the between-group difference at 4 months (primary endpoint), but also to evaluate in secondary analyses whether between-group differences are maintained over time (at 6 and 12 months). Results will be summarized as least-squares means (and their 95% confidence interval) within and between groups. The primary analysis will be conducted at significance level 0.05.

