Sensitivity Analyses. If there is heterogeneity in therapist-specific time trends, then our primary analysis may have an inflated Type 1 error rate. As a first sensitivity analysis, we will use the 4-month outcome as the dependent variable in a mixed model ANCOVA. The model will have fixed effects for treatment, site, gender, baseline BPI interference, and a therapist random effect. To deal with missing data, this analysis will be applied to multiple imputed datasets (see Missing Data Sensitivity Analyses section). We will check whether the conclusion from this analysis regarding the treatment effect is consistent with the conclusion from the primary analysis.

As a second sensitivity analysis, we will use a mixed model similar to the primary analysis model, except that time will be treated as continuous. We will check the linear time assumption by considering other polynomials (e.g. quadratic, cubic).

Secondary Analyses. We will use Holm's correction to adjust for multiple secondary analyses. We will also conduct a per protocol analysis as an adjunct to the ITT primary analysis defining a "dose" of treatment as having attended/answered calls for 3 treatment sessions.

IVR-collected data. Analysis of the continuous secondary outcomes collected by IVR (PEG-3, PHQ-8, Pain Catastrophizing Scale, Insomnia Severity Index, Pain Self-Efficacy Scale,) will be similar to the primary analysis. We will use a generalized mixed model for ordinal data to analyze the Patient Global Impression of Change outcome.

We will compare treatment dose (number of sessions, a count variable) and treatment satisfaction at 4 months (continuous) between groups by using a negative binomial generalized linear mixed model and linear mixed model, respectively. The models will include treatment, site and gender as fixed effects, and a random effect for therapist.

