Propensity score exploratory analysis. If the sample size allows, we will perform an analysis of the primary outcome (4-month BPI interference) that takes into account the type of treatment received in the synchronous CBT-CP group, that is, the treatment variable will be a 3-level categorical variable: video/telephone CBT-CP, in-person CBT-CP and COPES. This analysis will allow us to compare the two types of CBT-CP against each other and separately against COPES. To balance these three groups in terms of baseline covariates, we will use inverse probability of treatment weighted estimation based on propensity scores. The weights will be estimated from generalized boosted models and the estimates will represent population average treatment effects. At a minimum, the propensity models will include demographics, baseline values of the outcomes, and baseline medical and mental health comorbidities. Balance among treatment groups will be evaluated by standardized differences, with values >0.1 indicating imbalance. To deal with missing data, this analysis will be applied to multiple imputed datasets (see Missing Data Sensitivity Analyses section).

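### The per-protocol comparison selects on a dose the plan expects COPES patients to reach more often, with no adjustment for that selection, so it can show a difference between equally effective treatments.

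*Combined protocol and SAP*

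**What the plan says.** Under Secondary Analyses, Section 9.6 states: "We will also conduct a per protocol analysis as an adjunct to the ITT primary analysis". It defines a dose "of treatment as having attended/answered calls for 3 treatment sessions". That is the whole specification. No exclusion sentence, model, adjustment for selection or estimand follows.

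The Primary Analysis paragraph of Section 9.6 sets the covariate rule: "The only covariates that will be included in the primary and secondary analysis (including subgroup analyses) are site and gender". Its reason is: "We are adjusting for these 2 variables because they are used for stratification in randomization". Baseline BPI interference is modelled as a response, and "we will impose the constraint that the means for the two groups are equal at baseline", because the trial is randomised.

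On dose, Section 9.4 says: "We assume that dose will be greater in the IVR condition". Its table of monitored indicators includes the percentage reaching 3 sessions or weeks, and the text expects the monitored factors to favour IVR. It gives no percentages. Section 2.2 reports that IVR patients in the earlier efficacy trial received 2.3 more weeks of treatment (95% CI 1.0 to 3.6). Under Section 5.4, a COPES week counts if at least one call is answered that week, while control dose is the number of sessions attended.

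For another non-randomised contrast (video/telephone CBT-CP, in-person CBT-CP and COPES), the propensity score paragraph of Section 9.6 says: "we will use inverse probability of treatment weighted estimation based on propensity scores", with weights from boosted models. Nothing similar is planned for the per-protocol analysis.

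**The concern.** Reaching 3 sessions happens after randomisation and may depend on the arm. If the control hurdle is harder to clear, the control per-protocol set is the more selected one. If patients who clear it also tend to have a better prognosis, the two sets differ in prognosis before any treatment effect.

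Site and gender were chosen as stratification factors, not as predictors of adherence or outcome. Baseline depression, self-efficacy, comorbidity and distance to the facility are collected (Section 6.2.2) but would stay unbalanced. The argument that justifies equal baseline means also does not carry over to a selected subset.

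The result will be read beside the ITT estimate. If adherence relates to prognosis alike in both arms, the distortion grows with the dose advantage that motivates the trial, and COPES could wrongly look worse among treated patients.

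**Working it through.** **The plan's own figure.** Section 9.2 gives SD 2.4, a difference of 0.55, two-sided alpha 0.05 and 80% power. The required n per arm is 2 × (1.960 + 0.842)² × 2.4² / 0.55² = 299. With 305 per arm the power is 0.81. Allowing for 20% attrition, 305 / 0.8 = 381.25, so 382 per arm and 764 in total. The stated figures reproduce. The documents give no figure for the per-protocol analysis.

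**Inputs for the check.**
- From Section 9.2: SD 2.4, 305 patients per arm with outcomes, and 0.55 as the yardstick.
- Assumed: a baseline to 4-month correlation of 0.5. The residual SD after crediting the model with baseline BPI is 2.4 × √(1 − 0.5²) = 2.08.
- Assumed, because the documents give neither: the share p of each arm reaching 3 sessions, and the residual correlation ρ between propensity to reach them and a better 4-month score.
- True treatment effect: zero.

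**Formulas.** A patient enters the set if a latent normal propensity exceeds the cut-off that gives share p. The set's mean score is then lower (better) by ρ × 2.08 × λ(p), where λ(p) = φ(z)/p and z is the normal quantile of p. Hence:
- bias (COPES minus control; positive means COPES looks worse) = 2.08 × [ρ(control) × λ(control) − ρ(COPES) × λ(COPES)]
- SE = 2.08 × √[1/(305 × p for COPES) + 1/(305 × p for control)]

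The multipliers are λ(0.9) = 0.195, λ(0.8) = 0.350, λ(0.7) = 0.497 and λ(0.6) = 0.644.

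**Results with the same ρ in both arms.**

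| COPES vs control reaching 3 sessions | ρ | Bias (points) | SE | 5% test rejects |
|---|---|---|---|---|
| 80% vs 70% | 0.1 | 0.03 | 0.195 | 5% |
| 80% vs 60% | 0.2 | 0.12 | 0.203 | 9% |
| 80% vs 60% | 0.3 | 0.18 | 0.203 | 15% |
| 90% vs 60% | 0.2 | 0.19 | 0.199 | 16% |
| 90% vs 60% | 0.3 | 0.28 | 0.199 | 29% |

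Example: 0.3 × 2.08 × (0.644 − 0.350) = 0.18. Against 0.55, biases of 0.12 and 0.18 are 22% and 33%. With ρ = 0, or with equal shares and the same selection in both arms, the bias is zero.

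**Different ρ by arm, 80% vs 60%.** With 0.3 in COPES and 0.1 in control, the bias is 2.08 × (0.1 × 0.644 − 0.3 × 0.350) = −0.08, which favours COPES. The sign changes when the COPES correlation exceeds 0.644 / 0.350 = 1.84 times the control correlation.

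**Does handling baseline BPI suffice?** A simulation at 85% vs 60% (2,000 trials, correlation of propensity with outcome about −0.34) gave a bias of 0.31 unadjusted and 0.22 with baseline BPI handled, with rejection falling from 26% to 19%. The bias is reduced but not removed. ITT in the same runs was centred on zero.

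**Does weighting help?** A simulation at 80% vs 60% and ρ = 0.3 used stabilised weights fitted separately by arm (logistic, standing in for boosted models). If measured covariates carry half the residual confounding, the bias falls from 0.18 to 0.10 and rejection from 13% to 6%. If they carry all of it, the bias is 0.01. The SD of the estimate rises by 2% to 11%.

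**The case against.** A reader might infer that equal treatments will look different, and always to the disadvantage of COPES. The documents do not support that. Bias needs both unequal shares and a link between adherence and prognosis, and they quantify neither. The 2.3 extra weeks is a mean from a trial against in-person treatment, not a share reaching 3 sessions. Section 9.4 also concedes that home-based delivery to controls has weakened the case for superiority. Control attendance may be limited by therapist availability, travel or clinic hours, which may say little about prognosis, and the one-call rule may select a different kind of patient in COPES. The direction against COPES is therefore conditional.

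A reader might also infer that adjustment is strictly site and gender. If the primary model is reused, baseline BPI is handled too. The plan itself departs from the rule elsewhere, in the ANCOVA sensitivity analysis and in the missing-data analyses that add predictors of missingness. That the rule binds the per-protocol model is an inference from its place under Secondary Analyses. That the set excludes everyone below 3 sessions is likewise the ordinary meaning of the term, not a stated rule.

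Finally, the analysis is an adjunct that feeds no decision rule, the share reaching 3 sessions is already tracked by arm, and weighting cannot balance unmeasured motivation.

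These points limit the size, the certainty of direction and the consequence. They do not remove the problem: the plan expects unequal selection, allows little adjustment for it and says nothing about how to read the result.

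**Conclusion.** The concern holds in a conditional form. The per-protocol comparison can produce a difference between equally effective treatments. At 80% vs 60%, with an equal residual correlation of 0.2 to 0.3, the bias is 0.12 to 0.18 points against COPES and the 5% test rejects in 9% to 15% of trials. At 80% vs 70% with correlation 0.1 it is negligible. All shares and correlations are assumptions, as are the baseline correlation of 0.5 and the latent-normal form. The primary ITT test is untouched. The point is worth acting on because the remedy is cheap and the plan already contains the method.

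**What to change.** Amend the per-protocol sentence in Section 9.6 as follows.

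- State who is in the set. Keep the 3-session definition, and spell out what counts in each arm.
- Exempt this analysis from the site-and-gender rule. Drop the equal-baseline constraint for it and adjust for baseline BPI instead, for example with the 4-month ANCOVA form already given as the first sensitivity analysis.
- Weight each arm's set by the stabilised inverse probability of reaching 3 sessions. Estimate the weights separately by arm from baseline outcomes, demographics, comorbidities, distance and site, using the boosted-model approach of the propensity score paragraph.
- Report the share of each arm included and the baseline balance after weighting.
- Label the result non-randomised, with ITT taking precedence.

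The cost is SAP wording and a small analysis step on data already collected. The confidence interval becomes slightly wider, and only the part of the bias explained by measured predictors is removed.

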## **Interventions and Duration**

### COPES (IVR-CBT-CP)

Overview. COPES (IVR-CBT-CP) is a 10-week, IVR-facilitated program of CBT for chronic pain. The primary components of the intervention include: 1) a self-help handbook containing the rationale and instructions for using eight pain self-management skills, and their corresponding weekly skill practice goals; 2) a pedometer-facilitated walking program; 3) daily, automated IVR calls to collect patient-reported pain intensity and pain interference, sleep quality, pedometer-measured step count, and adherence to the pain coping skill practice ratings; and 4) weekly, two to four minute pre-recorded, personalized therapist messages based on participant IVR-reported data. The COPES IVR system provides participants the ability to automatically connect to the Veteran Crisis Line during any call. In this study, COPES will be centrally delivered from the VA Connecticut site. Participants will be given up to 14 weeks to complete treatment to allow for missed sessions (vacations, illness).

Intake and materials. Each weekly IVR module will feature a single self-management skill (e.g., paced physical activity, stretching, or relaxation) reinforced via a companion chapter in the patient handbook. The handbook, developed for the initial COPEs efficacy trial and refined prior to the ongoing COPEs implementation trial, is written at the 6th grade reading level and features design strategies to enhance engagement and readability. The manual will assign a specific goal each week that promotes practice of the module's coping skill (e.g., practice deep breathing for 5 minutes each day this week). The participant will be instructed to practice that week's skill each day of the week and report via daily IVR assessment their daily skill practice completion (0=not at all completed to 10=totally completed). Participants will have access to a patient handbook through the COPEs website. If patients do not have Internet access the handbook will be mailed to them. Participants will also be mailed an Omron Go Smart Model HJ-112 pocket pedometer to facilitate their participation in the walking portion of the treatment.

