Centralized intervention delivery. COPEs will be delivered from VACHS to all study sites. No additional clinicians will be placed in the study sites. Drs. [name], [name], and [name] all have experience delivering COPEs in one of our current or previously funded trials and will train new COPEs therapists. Because COPEs can be delivered centrally, by a core group of therapists who receive consistent training and use therapist manuals and feedback scripts to further standardize treatment provision, COPEs can be provided with a high degree of fidelity to the original treatment and is less subject to drift than synchronous treatments. After therapists complete the training period, we will monitor treatment fidelity and provide specific feedback to therapists regarding their delivery of the intervention in 30% of treatment sessions. We will track participant participation (number of weeks engaged) and treatment completion (yes/no), time to first treatment session, dose, time to treatment completion, and treatment fidelity.

Synchronous CBT-CP. VHA Evidence-Based Psychotherapy CBT-CP (referred to as in person CBT-CP) is a 10-session intervention containing skills similar to those contained in COPEs (IVR- CBT-CP). In general, patients attend weekly, individual, 50-minute treatment sessions with a previously trained CBT-CP therapist. We anticipate that given the COVID-19 pandemic local adaptation of CBT-CP will be common. We will not attempt to influence how synchronous CBT-CP is provided and will accept a number of common treatment provision methods including individual and group in-person, telephone, VVC, Zoom, Skype and other platforms accept by VA. We will carefully track through electronic record review treatment type, fidelity, and treatment engagement. A fidelity checklist is in the process of being developed. A detailed therapist manual provides pain education, case examples, and session by session guidance on treatment delivery. Following an initial assessment session, patients learn one pain coping skill

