*Substance Use Diagnosis.* We will abstract from each participant's VA electronic health record current (in the past 12 months) and past diagnosis of alcohol use disorder (diagnosis prior to the past 12 months).

*Synchronous treatment characteristics.* A trained research assistant will review each participant's electronic medical record at the completion of treatment to collect treatment characteristics, (platform, mode), time to treatment, treatment dose, time to completion, completion (y/n), and treatment quality.

IVR-collected outcome data. In addition to passively collected EHR data, we will actively collect patient-reported outcome data using automated IVR calls at baseline, 1, 4, 6, and 12 months. COPEs patients will receive regular IVR assessments as part of the COPEs intervention. At the baseline and follow-up periods they will be asked to complete the outcomes assessment at the end of a regularly scheduled call. CBT-CP patients will be enrolled in the IVR system after randomization and scheduled for assessment calls at baseline, 1, 4, 6, and 12 months. They will be informed of the 5-10 minute automated telephone interview to assess their pain and physical and emotional functioning, sleep, and satisfaction with their pain care at baseline and in 1, 4, 6 and 12 months. All measures demonstrate strong psychometric properties. IVR assessment allows us to collect outcomes data in a pragmatic, low burden manner, with no need for an in-person visit. We will not reimburse participants for cellphone minutes.

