### **6.2.4 Follow up Visits**

Follow-up information will be collected by the IVR system; there will be no in-person visits. With the exception of demographic data and treatment satisfaction, outcomes and covariates described in the baseline will be assessed at 1, 4, 6, and 12 months post-baseline. The four-month outcome will be the primary outcome. Follow-up assessments may be collected anytime within the window of 1 week prior to the planned assessment date to one month after. In order to minimize missing data, when participant do not complete the planned IVR assessment we will attempt to collect the information using telephone interview or survey mailing to the participant's home.

Various domains of pain treatment satisfaction will be assessed using a subscale of the Patient Outcomes Questionnaire at the four month outcome timepoint. This 5-item measure shows good internal consistency and significant associations with staff and patient ratings of patient improvement.

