## **8. INTERVENTION DISCONTINUATION**

If the principal investigator decides that a participant is not appropriate for the study, they could be withdrawn from the study intervention, even if they want to continue. However, consistent with an intention-to-treat study, participants will not be removed from study follow-up. This could happen if a participant no longer meets the requirements for the study, if participants are not able to do things required by the study, if it becomes medically unsafe for them to continue, or if approval to conduct the study is withdrawn. Regardless of whether or not the participant is withdrawn from this study, they will still get medical care as usual from their VA healthcare team. Withdrawal from the study does not result in any risk to the patient, thus no special procedures are planned for those who choose to withdraw on their own or who are withdrawn from the study by the PI.

Participation in this study is entirely voluntary. If a participant chooses not to enroll or withdraw after the participant has started, he/she will not be penalized in any way, nor will the quality of care received be affected. If a participant should choose to re-enroll after withdrawing, they may if they are still eligible. They may participate in the intervention up to the 14-week from baseline cutoff. If the participant decides not to participate in this study, the Veteran may receive CBT for pain or similar treatment at the local VA Healthcare System, though may need to come to the medical center for appointments rather than receive treatment by phone.

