## 9.5 Outcomes

### 9.5.1 Primary Outcome

Our primary outcome will be the interference subscale of the Brief Pain Inventory (BPI) score at 4 months post-baseline, which is a measure of patient-reported pain-related interference (0-10 scale, with higher values indicating more pain) and has been shown to be sensitive to change and to have good reliability. This outcome will be collected via the IVR automated call system.

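### The three-session per-protocol rule has no date limit, so sessions held after the month-4 assessment can qualify synchronous patients but essentially no COPES patients

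*Combined protocol and SAP*

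**What the plan says.** The primary outcome is the "interference subscale of the Brief Pain Inventory (BPI) score at 4 months post-baseline" (section 9.5.1). Section 9.6, under Secondary Analyses, states: "We will also conduct a per protocol analysis as an adjunct to the ITT primary analysis". The criterion for having been treated follows in the same sentence: "defining a 'dose' of treatment as having attended/answered calls for 3 treatment sessions". Section 9.3 covers intention-to-treat only and defines no per-protocol population that could supply a date.

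The two arms have different treatment clocks:

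- **COPES.** "Participants will be given up to 14 weeks to complete treatment to allow for missed sessions" (précis, Interventions and Duration; repeated in section 5.1).
- **Synchronous CBT-CP.** Patients go through a local consult (section 4.3). The précis says "We will not attempt to influence how synchronous CBT-CP is provided". No maximum wait or duration is stated. Under Synchronous treatment characteristics in section 6.2.2, a research assistant reviews each participant's "electronic medical record at the completion of treatment to collect treatment characteristics", and dose is among the items collected.

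Three other places bear on timing:

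- Section 6.2.4: "Follow-up assessments may be collected anytime within the window of 1 week prior to the planned assessment date to one month after".
- Section 8, on people who withdraw and then re-enrol: "They may participate in the intervention up to the 14-week from baseline cutoff". No arm is named.
- Section 9.5.2 lists treatment dose next to treatment satisfaction, followed by a parenthesis restricting collection to month 4. It is unclear whether the parenthesis covers both or satisfaction alone.

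Section 9.4 expects COPES patients to start treatment sooner than synchronous patients but gives no figure.

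**The concern.** Exposure that follows an outcome cannot have influenced it. A per-protocol set for a month-4 outcome should therefore depend only on treatment received before month 4. The rule does not say so, and the gap acts on one arm only. A synchronous patient first seen in month 5 who then attends three sessions meets the rule, although no treatment preceded the month-4 score. A COPES patient has in practice no such route.

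If such patients are included, the synchronous per-protocol mean is pulled towards an untreated mean while the COPES mean is not, so the shift favours the trial's superiority hypothesis. With the window unstated, the choice would also fall to the analyst after the session data are known.

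**Working it through.** **1. The plan's own figure.** With SD 2.4, difference 0.55, two-sided alpha 0.05 and 80% power (section 9.2), n per group = 2 × (1.960 + 0.842)² × 2.4² / 0.55² = 299. The plan states 305, which gives 80.8% power. Then 305 / 0.8 = 381.25, rounded up to 382 per group, or 764 in total. The sample size reproduces. It is for the intention-to-treat comparison; no size is given for the per-protocol set.

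**2. Calendar, counted from baseline.**

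- Month 4: 4 × 365.25 / 12 = 121.75 days, or 17.4 weeks.
- Assessment window (section 6.2.4): about day 115 to day 152, the latter being 21.7 weeks.
- COPES limit: 14 × 7 = day 98, which is 24 days before month 4. If the 14 weeks start only after the 7-day baseline calls, the limit is day 105, still before the window opens.
- Synchronous arm: no limit stated. For a third session by month 4, the first must fall by week 17.4 − 2 = 15.4 if sessions are weekly, or week 17.4 − 4 = 13.4 if they are two weeks apart.

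**3. Share of the synchronous set affected (assumed inputs).** Assume that the wait to first session is lognormal with median m and log-SD 0.6, that sessions are g = 1 or 2 weeks apart, and that every patient counted eventually reaches three sessions. With the assessment at week T, the share whose third session falls after it is

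1 − Φ( ln[(T − 2g)/m] / 0.6 ).

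For example, with T = 17.4, m = 8 and g = 1: ln(15.39/8) / 0.6 = 1.09, giving 13.8%.

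| Assumed median wait | Fewer than 3 sessions by week 17.4 | No session by week 17.4 | Fewer than 3 sessions by week 21.7 |
|---|---|---|---|
| 4 weeks | 1–2% | 0.7% | 0.4–0.7% |
| 8 weeks | 14–20% | 10% | 7–9% |
| 12 weeks | 34–43% | 27% | 20–26% |

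Ranges run from weekly to two-weekly sessions. With log-SD 0.7 and sessions counted to 12 months, the week-17.4 shares are 1–2%, 9–12%, 22–28% and 35–43% at median waits of 3, 6, 9 and 12 weeks.

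**4. Effect on the comparison (assumed inputs).** If a fraction f of the synchronous set is untreated at month 4, and treatment would have lowered BPI interference by E points, the per-protocol difference shifts towards COPES by f × E. Taking E as 0.5 to 1.5:

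- f = 10%: 0.05 to 0.15 points, or 9% to 27% of the 0.55 design difference.
- f = 20%: 0.10 to 0.30 points, or 18% to 55% of it.

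This takes the affected patients as wholly untreated; those with one or two sessions by month 4 would contribute less. It also ignores other differences between early and late starters.

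**The case against.** The strongest reply is that the plan is silent, not open-ended. A reader might infer that it counts synchronous sessions without limit and that untreated patients will be analysed as treated. No section says that. It is what the rule permits if applied literally, and a sensible analyst might impose a cut-off. This stands, and the point is worded accordingly.

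A reader might also infer that the secondary dose outcome compares a 14-week count with an unlimited one. Section 9.5.2 prevents that conclusion, because its parenthesis may already restrict dose to month 4. The schedule in section 6.1 points the other way: it marks satisfaction at month 4 and lists dose under EHR data with no month. The matter is unresolved. Either way, section 9.5.2 concerns the dose outcome and not the per-protocol criterion.

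Two other places might seem to supply a cut-off. Section 8 refers to a 14-week limit as if it already existed, but in a sentence about re-enrolment, and it is not tied to the per-protocol rule. Sections 5.4 and 9.6 collect attendance with the post-treatment adverse-event chart review, and section 10.3.4 places chart reviews at months 4, 6 and 12. That governs when data are gathered, not which sessions count.

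Nor do the documents show that late starts are common. Section 9.4 gives a direction only, and the assumed waits span almost none to a large minority. Finally, this is an adjunct analysis, and delayed access is part of what a pragmatic trial compares. That is true, but the intention-to-treat analysis already captures delayed access. It does not justify letting later sessions define who was treated when the outcome was measured.

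**Conclusion.** The point holds as an unstated counting window that acts on one arm. As written, sessions after the month-4 BPI measurement can admit synchronous patients, and essentially no COPES patients, to the per-protocol comparison; the resulting tilt would favour COPES. About 1% to 43% of the synchronous set would have fewer than three sessions by week 17.4 under assumed median waits of 4 to 12 weeks, and about 0.4% to 26% if the assessment falls at the late edge of its window. These figures are illustrations; no waiting time or session spacing is documented.

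The conclusion uses the post-baseline clock of sections 6.2.4 and 9.5.1. The précis and section 3 instead count follow-up from the start of treatment, and section 4.3 from its completion. The intention-to-treat primary analysis and the sample size are unaffected. No direction of bias is established for the dose outcome until section 9.5.2 is clarified.

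**What to change.** In section 9.6, state that only sessions or weeks occurring before the participant's month-4 assessment count towards the three-session criterion, in both arms. If that assessment is missing, use 4 months from randomisation. For the secondary dose outcome, state whether the month-4 restriction in section 9.5.2 applies to dose. Reconcile sections 6.2.2, 8, 9.5.2 and 9.6 so that one counting window applies to both arms. This concerns counting only and says nothing about how long treatment should last.

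The cost is SAP wording. Section 10.3.5 already provides for the number and timing of synchronous sessions to be taken from the record, and the IVR system holds the COPES call data. The downsides are a somewhat smaller synchronous per-protocol set, selected towards earlier starters, and exposure windows that vary by up to about five weeks with the assessment date. Both should be acknowledged when the analysis is reported.
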